- CC Arm: 40 subjects, *ad libitum* use of their preferred CC brand.
- SA Arm: 40 subjects who will abstain from smoking.

Subjects will be informed of their randomized study arm by the study site collaborator on Day 1 prior to 06:30 AM.

- Exposure period (from Day 1, 06:30 AM until Day 5, 11:00 PM):

The exposure period will consist of 5 days of *ad libitum* use of the assigned product between 06:30 AM and 11:00 PM in THS 2.2 and CC arms. Use of any tobacco/nicotine containing product other than the assigned product will not be allowed and may, at the discretion of the Investigator, result in the subject withdrawal from the study.

Subjects in the SA arm will be asked to abstain from smoking any nicotine/tobacco containing product and will not be provided with medication to support SA.

The end of the 24-h urine collection period for Day 5 will end in the morning on Day 6 prior to Discharge.

- Day of Discharge (Day 6) (from Day 5, 11:01 PM to time of Discharge):

Procedures of Discharge, including but not limited to laboratory parameters, will be conducted to discharge the subject from the clinic after 9 days in a confined setting. Use of CC will be allowed on Day 6, but only after spirometry has been performed.

- Safety follow-up period (from the time of Discharge on Day 6 to Day 13):

After time of Discharge, subject will enter a 7-day safety follow-up during which there will be recording of spontaneously reported new AEs/SAEs and the active follow-up of ongoing AEs/SAEs by the study site. In general, all AEs will be followed until resolved, stabilized (i.e., no worsening of the event), or a plausible explanation for the event has

been found. The end of the study is defined as the time of Discharge on Day 6 plus 7-day follow-up period.

During the study, any subjects who want to quit smoking will be encouraged to do so, and will be referred to medical services and will be withdrawn from the study. This is applicable for all subjects during screening to the baseline period and for subjects allocated to THS 2.2 or CC arms during the exposure period.

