6.6 Restrictions

6.6.1 Smoking Restrictions and Restrictions to the Smoking Abstinence Arm

To avoid cross contamination between the 3 study arms, subjects must use THS 2.2 and CC must in separate rooms and subjects allocated to the SA arm should not have access to the smoking rooms. All precautions should be taken to remove any temptation to smoke for subjects who are randomized to the SA study arm.

In the THS 2.2 and SA arms, subjects will not be allowed to smoke any CC or use any nicotine/tobacco containing products (including NRT) from Day 1 (06:30 AM) until Day 5 (11:00 PM). In the CC arm, subjects will not be allowed to use the THS 2.2, any nicotine/tobacco containing products and other CC than collected to the site by the subject.

During the confinement period, smoking will generally only be allowed during the designated smoking times, from 06:30 AM to 11:00 PM. Smokers will not have free access to their CC or THS 2.2; these will be dispensed by the study site collaborator individually as described in Section 6.5.1.

Smoking will not be allowed during assessments on the Admission Day at the discretion of the site. Smoking is also not allowed from Day 5, 11:00 PM until the spirometry has been performed on Day 6.

In general, the performance of scheduled procedures has priority over the wish of a subject to smoke. However, this is different at Day 5 due to the assessment of the nicotine profile. If the subject wants to smoke at Day 5 around the time of the blood draw, he/she should inhale/smoke first and the blood will be drawn after the tobacco stick/cigarette has been inhaled/smoked.

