7.5.1 Biomarker of Exposure

7.5.1.1 Exhaled CO and Carboxyhemoglobin

Carboxyhemoglobin measured in blood and exhaled CO will be investigated as a measure of CO in all three study arms. The CO breath test should be conducted in timely conjunction with the blood sampling for COHb, where applicable. In the SA arm, the CO breath test will serve as a verification of compliance (Section 6.5.4).

CO Breath Test

Carbon monoxide in exhaled breath will be measured using the Smokerlyzer[®] such as Micro 4 Smokerlyzer[®] device or similar.

On Days -1 to Day 5, the CO breath test will be conducted four times per day. The first test should be conducted within 15 minutes prior to the first product use. The other three tests should be conducted as described in section 9.

Confidentiality statement: Data and information contained in this document are considered to constitute trade secrets and confidential commercial information, and the legal protections provided to such trade secrets and confidential information are hereby claimed under the provisions of applicable law. No part of this document may be publicly disclosed without the written consent of Philip Morris Products S.A.

For subjects in the SA arm, the first CO breath test will be done between 08:00 AM-09:30 AM. The other three tests should be conducted as described in section 9.

On Day -2, Day 6, the CO breath tests will be conducted once irrespective of time of product use.

Carboxyhemoglobin

Assessment for COHb measurement will be performed at the local laboratory. Carboxyhemoglobin in blood will be assessed on a daily basis, starting from Day -1 until Day 5.

On Day -1 to Day 4: one blood sample will be collected between 08:00 PM-09:30 PM.

On Day 5: one blood sample will be collected within 15 minutes prior to the first product use. The three other blood samples will be collected as described in section 9.

For subjects in the SA arm, the first COHb will be done between 08:00 AM-09:30 AM. The three other blood samples will be collected as described in section 9.

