	√	CYP2A6 activity in plasma	To be done prior to smoking.
		Assessment of cough (VAS)	To be done prior to smoking but not later than 10:00 AM.
		MNWS questionnaire	To be done prior to smoking but not later than 10:00 AM .
		Spirometry without short-acting bronchodilator	To be done prior to smoking
		CO breath test	To be done within 15 minutes prior to smoking
		HST	HST SODIM® device has to be used for all product uses if compatible CCs are smoked
06:30 AM		Beginning of smoking period	
	√	Clinical laboratory parameters (hematology, clinical chemistry)	In at least 10 hours of fasted condition
	√	Bio-banking for transcriptomics (if consent is obtained)	In at least 10 hours of fasted condition .
	√	Bio-banking for BoExp/ risk markers in serum/plasma (if consent is obtained)	In at least 10 hours of fasted condition
		Urine safety analysis	
Before 10:00 AM		Breakfast	

Confidentiality statement: Data and information contained in this document are considered to constitute trade secrets and confidential commercial information, and the legal protections provided to such trade secrets and confidential information are hereby claimed under the provisions of applicable law. No part of this document may be publicly disclosed without the written consent of Philip Morris Products S.A.

Time	Blood sample	Procedures	Additional information
Start of procedure		Baseline Day 0	
10:00 AM-11:30 AM		Vital signs (blood pressure, pulse rate, respiratory rate)	At least 5 minutes in supine position prior to measurement
10:00 AM-11:30 AM		A caffeine tablet containing around 170 mg of CAF with 150 ± 10mL water	
12:00 PM-01:30 PM		CO breath test	
Before 02:30 PM		Lunch	
04:00 PM-05:30 PM	√	CYP1A2 activity in plasma	6 hours +/-15minutes after intake of caffeine tablet
04:00 PM-05:30 PM		CO breath test	
Afternoon		Snacks	
In the evening until 09:00 PM		Dinner	
08:00 PM-09:30 PM		CO breath test	
08:00 PM-09:30 PM	√	COHb in blood	
08:00 PM-09:30 PM	√	Nicotine, cotinine in plasma	
08:00 PM-09:30 PM		HST questionnaire	
08:00 PM-11:00 PM		MCEQ questionnaire, QSU-brief questionnaire	
11:00 PM		End of smoking period	

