9.2.3 Exposure Period (Days 1 to 5)

The tables in this Section show the assessments that will be performed during the confinement period (Day 1 to Day 5). Table 10 shows the assessments that will be performed on Day 1:

Table 10. Time Schedule – Day 1

Time	Blood sample	Procedures	Additional information
Start of procedure		Day 1	
		AE/SAE recording; concomitant medication	All day
		Support during smoking abstinence (SA arm only) if needed	All day
Before 06:30 AM		Subjects are informed of their assigned study arm.	
6:29 AM+/-20min		Analysis sample to be taken after final portion of urine has been added to Day 0 sampling bottle. Must be prior to first product use of Day 1	BoExp, creatinine, and Ames mutagenicity in 24-hour urine Risk markers: 8-epi-PGF2 α and 11- DTX-B2 Bio-banking for BoExp/ risk markers in 24-hour urine (if additional consent is obtained)

Confidentiality statement: Data and information contained in this document are considered to constitute trade secrets and confidential commercial information, and the legal protections provided to such trade secrets and confidential information are hereby claimed under the provisions of applicable law. No part of this document may be publicly disclosed without the written consent of Philip Morris Products S.A.

Time	Blood sample	Procedures	Additional information
Start of procedure		Day 1	
6:30 AM+/-20min		Start collection to Day 1 sampling bottle	
		Assessment of cough (VAS)	To be done prior to product use but not later than 10:00 AM
		MNWS questionnaire	To be done prior to product use but not later than 10:00 AM
		CO breath test	Within 15 minutes before first product use (for THS 2.2 and CC arms) or between 08:00 AM-09:30 AM (SA arm)
06:30 AM-11:00 PM		HST	In THS 2.2 and CC arms, HST SODIM [®] device has to be used for all product uses if compatible CCs are smoked
6:30 AM		Beginning of product use	
Before 10:00 AM		Breakfast	
10:00 AM-11:30 AM		Vital signs (blood pressure, pulse rate, respiratory rate)	At least 5 minutes in supine position prior to measurement
12:00 PM-01:30 PM		CO breath test	
Before 02:30 PM		Lunch	
04:00 PM-05:30 PM		CO breath test	
Afternoon		Snacks	
In the evening until 09:00 PM		Dinner	
08:00 PM-09:30 PM		CO breath test	
08:00 PM-09:30 PM	√	COHb in blood	
08:00 PM-09:30 PM	√	Nicotine, cotinine in plasma	
08:00 PM - 11:00 PM		MCEQ questionnaire (THS 2.2 and CC arms only), QSU-brief questionnaire	

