**Table 16: Assessment Windows**

Assessment	Nominal Time point(s)	Window
CO breath test	Day -2 and Day 6 Morning (Days -1 to 5)	Irrespective of product use To be done within 15 minutes prior to product use (for THS 2.2 and CC arms) or between 08:00 AM and 09:30 AM (SA arm)
	Day -1 to Day 5	Between 12:00 PM and 01:30 PM, 04:00 PM and 05:30 PM, and 08:00 PM and 09:30 PM
Assessment of Cough	Day 0 to 6	To be done prior to smoking/product use but not later than 10:00 AM.
MNWS Questionnaire	Day 0 to 6	To be done prior to product use but not later than 10:00 AM
QSU-brief questionnaire	Day -1 to 5	08:00 PM to 11:00 PM
MCEQ questionnaire	Day -1 to 5	08:00 PM to 11:00 PM
Nicotine and cotinine in plasma	Day 0 to Day 4 (all study arms) between 08:00 PM and 09:30 PM	
	Day 5 (THS 2.2 and CC arms) within 15 minutes before first product use (T_0): then additional blood samples at 2 hour intervals from T_0 until 11:00 PM.	Each sample has a 5 minute time window
	Day 6 (THS 2.2 and CC arms): 20 and 24 h after T_0 of Day 5 Day 5 and Day 6 (SA arm): On Day 5, between 08:00 PM and 09:30 PM. On Day 6, between 08:00 AM and 9:30 AM.	5 minute time window
COHb blood Sampling	Days -1 to 4 Morning sample on Day 5	8:00 PM to 09:30 PM Within 15 minutes prior to product use (for THS 2.2 and CC arms) or between 08:00 AM and 09:30 AM (SA arm)
	Day 5 other samples	Between 12:00 PM and 01:30 PM, 04:00 PM and 05:30 PM, and 08:00 PM and 09:30 PM

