12.6.2 Secondary Analyses

12.6.2.1 Biomarkers of Exposure

In addition, the quantity excreted over 24 hours for MHBMA, 3-HPMA and S-PMA will be presented.

The PP Population will be used to examine the robustness of the analysis of the primary endpoints. The primary analysis on the FAS will be repeated on the PP population using the same methodology as detailed in Section 12.6.1.1 “Primary Biomarkers of Exposure in 24 hour collection”.

The primary BoExp will also be examined to compare the reductions in THS 2.2 vs. SA using the same methodology as for the primary analysis.

The secondary BoExp are exhaled CO, total 1-OHP in urine, Total NNN in urine, 4-ABP in urine, 1-NA in urine, 2-NA in urine, o-tol in urine, CEMA in urine, HEMA in urine, B[a]P in urine, HMPMA in urine, S-BMA in urine, Total NNAL in urine and NEQ in urine. The urine parameters will be expressed as concentrations adjusted for creatinine and the quantity excreted over 24 hours.

The baseline of the exhaled CO will be the time-matched measurements on Day 0, i.e. the 1st measurement on Days 1 to 5 will be matched to the 1st measurement on Day 0 and similarly for the 2nd, 3rd and 4th measurements. The baseline of the urinary biomarkers will be the last assessment prior to 06:29 AM on Day 1.

The values and percent changes for urinary BoExp in the quantity excreted over 24-hours and the concentration adjusted for creatinine will be listed and summarized. In addition line graphs will be produced for product means (and 95% CI) over all timepoints.

CO in exhaled breath will be measured using the Micro+™ Smokerlyzer® or similar device, conducted on Day -2 to Day 6. On Day -1 to Day 5 the first test per day will be performed within 15 minutes prior to the first product use and then between 12:00 and 01:30 PM, between 04:00 and 05:30 PM and between 08:00 and 09:30 PM. On Days -2 and Day 6 the CO breath tests will be conducted once.

Descriptive statistics summarized by exposure will be produced separately for all timepoints for all visits applicable for exhaled CO. This will be done on the FAS, stratified by sex, and CC consumption.

Actual values and percent changes from baseline in levels of exhaled CO will be listed and summarized. In addition line graphs will be produced for product means (and 95% CI) over all timepoints.

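### The SAP's time-matched exhaled-CO change is not time-matched for the first daily test in the SA arm, because that test is scheduled differently on Day 0 and on Days 1-5

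*SAP*

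**What the plan says.** **Matching rule.** SAP 12.6.2.1 sets a time-matched Day 0 baseline for exhaled CO by ordinal position: "the 1st measurement on Days 1 to 5 will be matched to the 1st measurement on Day 0". The second, third and fourth tests are paired in the same way. The resulting percent changes go to Table 15.2.4.12, whose title calls them time-matched.

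**Day 0.** Protocol Table 9 schedules the first CO test for all subjects: "To be done within 15 minutes prior to smoking". It has no SA exception. Protocol Table 8 does the same for Day -1.

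**Days 1 to 5.** Protocol Table 10 splits the first test by arm: "Within 15 minutes before first product use (for THS 2.2 and CC arms) or between 08:00 AM-09:30 AM (SA arm". Tables 11 to 14 repeat this. Protocol 7.5.1.1 agrees: "For subjects in the SA arm, the first CO breath test will be done between 08:00 AM-09:30 AM". SAP Table 16 carries the same alternative, "or between 08:00 AM and 09:30 AM (SA arm".

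**The SAP's own description.** SAP 12.6.2.1 nevertheless says of all arms: "On Day -1 to Day 5 the first test per day will be performed within 15 minutes prior to the first product use". SA subjects use no product on Days 1-5, so this cannot describe them, and it disagrees with SAP Table 16.

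**Disclosure and smoking hours.** Protocol 4.1: "Subjects will be informed of their randomized study arm by the study site collaborator on Day 1 prior to 06:30 AM". Protocol 6.6.1: "smoking will generally only be allowed during the designated smoking times, from 06:30 AM to 11:00 PM".

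**The concern.** A time-matched change is meant to remove the daily rhythm of CO, which falls overnight and rises with smoking. That works only if baseline and follow-up are taken at comparable points in the rhythm. For the SA first test the scheduling rule itself changes between Day 0 and Day 1, and in no other arm.

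On the morning of Day 1 all three arms share the same recent history: their own cigarettes, permitted until 11:00 PM on Day 0. Any arm difference in the first Day 1 reading that comes only from later sampling would sit in a table labelled time-matched, in the arm that serves as the reference point. The secondary objective of describing THS 2.2 against SA over the exposure period would then start from a comparison that is not like for like.

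**Working it through.** The plan states no figure for this offset, so there is nothing to reproduce. The check compares the windows and then illustrates the size.

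**1. The four daily tests**

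| Test | Day 0, all subjects | Days 1-5, THS 2.2 and CC | Days 1-5, SA |
|---|---|---|---|
| 1st | within 15 min before first cigarette | within 15 min before first use | 08:00-09:30 AM |
| 2nd | 12:00-01:30 PM | same | same |
| 3rd | 04:00-05:30 PM | same | same |
| 4th | 08:00-09:30 PM | same | same |

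Only the first test in SA changes its rule.

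**2. Can the SA window apply on Day 0?** SAP Table 16 labels the morning test Days -1 to 5, and footnote g of the Schedule of Events reads similarly. Taken literally, SA would have the later window at baseline too. That cannot operate: randomization may occur at any time on Day 0, arms are disclosed on Day 1, and the Day -1 and Day 0 schedules show no SA window.

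**3. Offset in hours.** Offset = SA follow-up time minus Day 0 first-test time.

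| Day 0 first test | Offset for SA at 08:00 | Offset for SA at 09:30 |
|---|---|---|
| 06:30 | +1.5 h | +3.0 h |
| 08:00 | 0 h | +1.5 h |
| 09:30 | -1.5 h | 0 h |

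Measured from the latest permitted cigarette at 11:00 PM, the 06:30 AM test is at 7.5 h and the SA test at 9.0-10.5 h.

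**4. Illustrative size on Day 1.** Two inputs are assumed. The first is a half-life h: the protocol (4.2) gives only an average of at most 24 h for the primary biomarkers, and nothing specific for exhaled CO. The second is an 11:00 PM level of 5.25 times background, taken as 2.10/0.40 from the COHb ratios in SAP Table 11 and used as a proxy for exhaled CO.

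Level at t hours after 11:00 PM, with background = 1: L(t) = 1 + 4.25 × 2^(-t/h).

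For h = 4: L(7.5) = 2.159, L(9) = 1.893, L(10.5) = 1.689. Then 1.893/2.159 - 1 = -12% and 1.689/2.159 - 1 = -22%.

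| h | Day 0 first test 06:30 (SA at 08:00; 09:30) | 08:00 (SA at 08:00; 09:30) | 09:30 (SA at 08:00; 09:30) |
|---|---|---|---|
| 4 h | -12%; -22% | 0; -11% | +12%; 0 |
| 6 h | -10%; -19% | 0; -10% | +11%; 0 |
| 8 h | -8%; -16% | 0; -8% | +9%; 0 |
| 24 h | -3%; -6% | 0; -3% | +3%; 0 |

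Without a background term, the fall is 1 - 2^(-gap/h). For gaps of 1.5 and 3 h that is 23% and 41% at h = 4, and 4% and 8% at h = 24. The size therefore depends on the model as well as on the half-life.

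**5. Day 2.** The SA first test is then 33-34.5 h after the last permitted cigarette, against 31.5 h at 06:30 AM. With h = 8: L(31.5) = 1.277, L(33) = 1.244, L(34.5) = 1.214, against a Day 0 baseline L(7.5) = 3.219. The later sampling moves the change by (1.244 - 1.277)/3.219, about -1 percentage point, to (1.214 - 1.277)/3.219, about -2 points. The true change at matched time is 1.277/3.219 - 1 = -60%, so genuine abstinence dominates from Day 2.

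**6. Which analyses use test 1.** SAP 12.6.2.1 uses the last exhaled-CO measurement in its ANCOVA, and that window is the same in all arms. SAP Section 9, however, says the COHb and exhaled-CO models include product-by-time-point terms, with the main comparison over all time points. Under that text test 1 would enter the comparison.

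**The case against.** The case for leaving the plan alone has several sound parts.

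- **SA needs its own window.** These subjects have no first use to anchor to, and the breath test also verifies abstinence. The window is disclosed in the protocol tables and SAP Table 16, and Listing 15.3.3.2 shows sampling times. This stands as a reason for the window. It does not make the pairing time-matched.
- **A 06:30 AM first cigarette is the earliest case.** Smoking is ad libitum. On Day 0 a CYP2A6 blood draw, spirometry, the cough assessment and the MNWS must all precede smoking, and the last two may run to 10:00 AM. This stands.
- **The other arms are matched on an event, not a clock time.** The Day 1 schedule has no spirometry or CYP2A6 draw before use, so their first use may come at a different hour from Day 0. This stands.
- **Reach is small.** The matched change has one named table. The listed CO figure, 15.1.2.4, shows mean levels; its title shows no baseline matching. This stands.

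A reader might infer that SA will show a spurious Day 1 fall of a known size while THS 2.2 and CC show none. The documents do not support that. The direction depends on each subject's Day 0 first-cigarette time, the size depends on a half-life they do not give, and no change in the other arms is not assured. Nor do they name the first Day 1 test as a null check; that is only how the shared history would lead one to read it.

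**Conclusion.** The point holds as a minor one. In the SA arm the first-test exhaled-CO change is labelled time-matched and is not, and SAP 12.6.2.1 disagrees with SAP Table 16 on when that test is taken.

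On Day 1 the offset is 1.5-3 h if the Day 0 first cigarette was at 06:30 AM, and zero or reversed if it was at about 08:00-09:30 AM. The 8-22% fall is an illustration only: it needs a 4-8 h half-life, a COHb planning ratio standing in for exhaled CO, smoking up to 11:00 PM and a 06:30 AM first use.

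The effect is confined to one of four daily tests, mainly on Day 1, in a descriptive table. No primary endpoint is affected, and neither is the Day 5 ANCOVA on the last test. The one route to a wider effect is SAP Section 9, which conflicts with 12.6.2.1 on whether all time points enter the exhaled-CO comparison.

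**What to change.** Either of two routes is enough.

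1. **Change the window (Protocol 7.5.1.1 and Tables 10-14; SAP Table 16).** Take the SA first test on Days 1-5 at the clock time of that subject's own Day 0 first test. Subjects are already up for the urine void shortly before 06:30 AM. The cost is one changed breath-test window in one arm. THS 2.2 and CC would still be matched on first use rather than on the clock, and the SAP should say so.
2. **Correct the SAP, for data collected at 08:00-09:30 AM.** State the SA window in 12.6.2.1, so that it agrees with Table 16. Leave the Day 1 SA first test out of the time-matched change; tests 2-4 stay matched. Keep the SA first test on Days 2-5 with a footnote to Table 15.2.4.12 giving the different window. The cost is a short text change and one fewer SA time point in a descriptive table. Matching that test by clock time is generally not possible, because Day 0 has no scheduled 08:00-09:30 AM test.

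Under both routes, limit the SAP Table 16 label for the SA window to Days 1-5. Reconcile SAP Section 9 with 12.6.2.1, stating whether the exhaled-CO comparison uses the last test or all time points and, if all, how the SA first test is handled.

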12.6.1 Primary Analyses

12.6.1.1 Primary Biomarkers of Exposure in 24 hour collection

The primary BoExp (COHb in blood and urinary concentrations adjusted for creatinine of MHBMA, 3-HPMA and S-PMA) will be summarized as detailed in Section 12.1.3 “Descriptive Statistics”.

The baseline is as defined in Section 12.1.4 “Definitions for Statistical Data Analysis”,

The values and percent changes in the concentration adjusted for creatinine will be listed and summarized along with the COHb concentrations and percent changes from baseline. In addition line graphs will be produced for means (and 95% CI) over all timepoints.

For all arms the 24 hour urine collection will be collected daily from Day -1 to Day 5. Although the 24 hour urine collection will span into the following Day it will be reported by the day the collection started.

The primary endpoints will be log-transformed (base_e) prior to analysis. The analysis will compare (1) last Day 5 values of COHb in blood and (2) urinary concentrations of MHBMA, 3-HPMA and S-PMA corrected for creatinine on Day 5 between the THS 2.2 and CC arms. An ANCOVA (Snedecor and Cochran 1982) model will be used with terms for the log-transformed baseline value, sex, average daily CC consumption over the last 4 weeks as reported during screening and product.

The SAS code to be used is shown below:

```
Proc mixed data=_data_ ;
Class product sex cigarette_cons ;
Model log (Day 5) = log (baseline) sex cigarette_cons product ;
Lsmean product / pdiff =control('CC') alpha=0.05 cl ;
Run ;
```

The least squares (LS) means and estimate of the difference along with it's 95% CI will be back-transformed before presenting in the tables. The geometric LS means for each product along with the ratio (THS 2.2 : CC) and 95% CI will be presented in the tables.

In addition line graphs will be produced for product means (and 95% CI) over all timepoints for COHb in blood and urinary concentrations adjusted for creatinine of MHBMA, 3-HPMA and S-PMA.

The data will be presented in the below outputs, the TFL number refers to the TFL number in the accompanying TFL shell document:

TFL number	Title
FIGURES	
15.1.1.1	Blood COHb (%) Mean and 95% CI– FAS
15.1.1.2	MHBMA Urinary Concentration Adjusted for Creatinine (units) Mean and 95% CI – FAS
15.1.1.3	3-HPMA Urinary Concentration Adjusted for Creatinine (units) Mean and 95% CI– FAS
15.1.1.4	S-PMA Urinary Concentration Adjusted for Creatinine (units) Mean and 95% CI– FAS

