The last measurement of exhaled CO will be used in the analysis. An ANCOVA model will be used with terms for the baseline value, sex, average daily CC consumption over the last 4 weeks as reported during screening and product. No adjustment will be made for multiple comparisons.

The analysis will compare the log-transformed urinary concentrations corrected for creatinine on Day 5 to 6 and the quantity excreted over 24-hours on Day 5 to 6 between the THS 2.2 and CC arms. An ANCOVA model will be used with terms for the log-transformed baseline value, sex, average daily CC consumption over the last 4 weeks as reported during screening and product. No adjustment will be made for multiple comparisons.

The SAS code will be the same as described in Section 12.6.1.1 “**Primary Biomarkers of Exposure in 24 hour collection**”.

LS means for each product along with the difference (THS 2.2 - CC) and 95% confidence interval (CI) will be presented in the tables.

The secondary BoExp will also be examined to compare the reductions in THS 2.2 vs. SA using the same methodology as above.

TFL number	Title
FIGURES	
15.1.2.1	Urinary MHBMA Quantity Excreted Over 24 hours Mean and 95% CI– FAS
15.1.2.2	Urinary 3-HPMA Quantity Excreted Over 24 hours Mean and 95% CI– FAS
15.1.2.3	Urinary S-PMA Quantity Excreted Over 24 hours Mean and 95% CI– FAS
15.1.2.4	Exhaled CO Arithmetic Mean and 95% CI– FAS
15.1.2.5	1-OHP Urinary Concentration Adjusted for Creatinine Mean and 95% CI– FAS
15.1.2.6	Urinary 1-OHP Quantity excreted Over 24 hours Mean and 95% CI– FAS
15.1.2.7	Total NNN Urinary Concentration Adjusted for Creatinine Mean and 95% CI– FAS
15.1.2.8	Urinary Total NNN Quantity Excreted Over 24 hours Mean and 95% CI– FAS

TFL number	Title
15.1.2.9	4-ABP Urinary Concentration Adjusted for Creatinine Mean and 95% CI- FAS
15.1.2.10	Urinary 4-ABP Quantity Excreted Over 24 hours Mean and 95% CI- FAS
15.1.2.11	1-NA Urinary Concentration Adjusted for Creatinine Mean and 95% CI- FAS
15.1.2.12	Urinary 1-NA Quantity Excreted Over 24 hours Mean and 95% CI- FAS
15.1.2.13	2-NA Urinary Concentration Adjusted for Creatinine Mean and 95% CI- FAS
15.1.2.14	Urinary 2-NA Quantity Excreted Over 24 hours Mean and 95% CI- FAS
15.1.2.15	o-tol Urinary Concentration Adjusted for Creatinine Mean and 95% CI- FAS
15.1.2.16	Urinary o-tol Quantity Excreted Over 24 hours Mean and 95% CI- FAS
15.1.2.17	CEMA Urinary Concentration Adjusted for Creatinine Mean and 95% CI- FAS

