15.3.3.2 Listing of Secondary Biomarkers and Sampling / Collection Times

12.6.2.1.1 Confirmatory Analysis

The hypothesis to be tested for each of the secondary BoExp is that the geometric mean level on Day 5 of the BoExp for THS 2.2 is lower relative to CC.

Analysis of the secondary BoExp will be conducted on the natural log scale. In order to test the follow hypothesis

$$\begin{aligned} \text{Null hypothesis (H}_0\text{):} & \quad m_1 \geq m_2 \\ \text{Alternative hypothesis (H}_1\text{):} & \quad m_1 < m_2 \end{aligned}$$

Where m_1 and m_2 are the geometric means of the BoExp levels on Day 5 for THS 2.2 and CC respectively.

The SAS code will be the same as described in Section 12.6.1.1 “Primary Biomarkers of Exposure in 24 hour collection”.

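### The SAP contradicts itself on the scale for exhaled CO and tabulates secondary biomarkers as differences, although the stated hypothesis concerns geometric means on the log scale

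*SAP*

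**What the plan says.** SAP 12.6.2.1 lists exhaled CO first among the secondary biomarkers of exposure and describes its model in these words: "The last measurement of exhaled CO will be used in the analysis. An ANCOVA model will be used with terms for the baseline value". Neither outcome nor baseline is logged. The next paragraph, on the urinary markers, is explicit: "The analysis will compare the log-transformed urinary concentrations corrected for creatinine on Day 5 to 6", with a log-transformed baseline as well.

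The section then points to the primary analysis for its program: "The SAS code will be the same as described in Section 12.6.1.1". That code reads "Model log (Day 5) = log (baseline) sex cigarette_cons product".

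For reporting, 12.6.2.1 states: "LS means for each product along with the difference (THS 2.2 - CC) and 95% confidence interval (CI) will be presented in the tables". The primary analysis in 12.6.1.1 states instead: "The geometric LS means for each product along with the ratio (THS 2.2 : CC) and 95% CI will be presented in the tables".

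Three other places bear on the point:

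- SAP 12.6.2.1.1 sets a geometric-mean hypothesis for each secondary biomarker and says: "Analysis of the secondary BoExp will be conducted on the natural log scale".
- Protocol 12.4.4, whose hypothesis covers primary and secondary biomarkers, puts the analysis on the natural log scale and has group differences back-transformed into relative effects.
- SAP section 9 lists departures from the protocol. A change of scale for CO is not among them. It does describe a CO analysis with a product-by-time-point interaction, in which the main comparison is over all time points rather than at the last measurement.

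**The concern.** Two adjacent and otherwise parallel paragraphs differ on whether logs are taken, so a programmer can defend either analysis of CO. The two answer different questions. The log model estimates a ratio of geometric means, which is what the hypothesis is about. The raw model estimates a difference in arithmetic means, in ppm.

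The raw model would also fit one residual variance to three arms whose CO levels should differ widely. SAP 12.6 puts all arms in every model. If spread rises with level, the CC arm has the largest variance but only 40 subjects, while the 120 subjects in the other two arms dominate the pooled estimate. The THS 2.2 versus CC interval would then look more precise than it is.

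The reporting sentence affects every secondary biomarker. A log-scale difference in a column labelled as a difference invites misreading: a ratio of 0.40 would appear as ln 0.40 = −0.92, not as a 60% reduction.

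**Working it through.** **Inputs.** Allocation is 80 THS 2.2, 40 CC and 40 SA (SAP section 8). No mean ratio or CV for exhaled CO appears in either document, so COHb is taken as a stand-in (assumption): THS 2.2/CC 0.40 with CV 0.32, and THS 2.2/SA 2.10 (SAP Table 11); THS 2.2/CC 0.44 with CV 0.14 (SAP Table 12, which has no SA ratio, so 2.10 is borrowed).

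**The plan's own figure.** SAP Table 13 gives power for the four primary markers. With log-scale SD = √ln(1 + CV²), COHb has SD √ln(1 + 0.32²) = 0.312 and SE 0.312 × √(1/80 + 1/40) = 0.0605. At a 50% reduction the effect is ln(0.50/0.40) = 0.223, and normal-approximation power is Φ(0.223/0.0605 − 1.96) = Φ(1.73) = 95.8%. The joint noncentral-t calculation over all four markers gives:

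| Reduction | 50% | 51% | 52% | 53% | 54% | 55% |
|---|---|---|---|---|---|---|
| Stated, YVD-CS01-EU | 96% | 91% | 85% | 75% | 63% | 48% |
| Recomputed | 95.5% | 91.4% | 84.8% | 75.2% | 62.8% | 48.5% |

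The row reproduces, so it is consistent with planning on the log scale with a constant CV. The ZRHX-EX-01 row does not reproduce at 52% and above with its CV of 0.14 (89, 68, 37 and 13% against 96, 81, 48 and 16%). Nothing below depends on that, because the CV cancels from the SE ratio.

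**If CO were analysed raw.** Set the CC mean to 1 and let SD = CV × mean in each arm. With the first set of ratios:

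- SDs: THS 2.2 0.40 × 0.32 = 0.128; CC 0.320; SA (0.40/2.10) × 0.32 = 0.061.
- Pooled variance: (79 × 0.128² + 39 × 0.320² + 39 × 0.061²)/157 = 0.0346.
- Model SE of THS 2.2 minus CC: √[0.0346 × (1/80 + 1/40)] = 0.0360.
- True SE: √(0.128²/80 + 0.320²/40) = 0.0526.
- Ratio: 0.0360/0.0526 = 0.69. Coverage of a nominal 95% interval: 2Φ(1.96 × 0.685) − 1 = 82%.

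With 0.44 and CV 0.14 the SEs are 0.0162 and 0.0232, the ratio is 0.70 and coverage is 83%.

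**Simulation with covariates.** Each scenario used 4,000 trials of the three-arm ANCOVA (baseline, sex, consumption stratum) on lognormal data, with baseline correlation 0, 0.5 and 0.8:

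| Stand-in | Raw-scale coverage | Log-scale coverage |
|---|---|---|
| 0.40, CV 0.32 | 82.0, 82.2, 83.0% | 95.6, 95.0, 95.1% |
| 0.44, CV 0.14 | 81.6, 81.8, 84.7% | 94.8, 94.2, 95.3% |

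**Range.** The true CO ratio is unknown, so it was varied with SA held at the THS 2.2 level divided by 2.10:

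| THS 2.2/CC | 0.2 | 0.3 | 0.4 | 0.6 | 0.8 | 1.0 |
|---|---|---|---|---|---|---|
| SE ratio | 0.63 | 0.66 | 0.69 | 0.76 | 0.83 | 0.90 |
| Coverage | 78% | 80% | 82% | 86% | 90% | 92% |

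If raw variances were equal across arms, the pooled variance would be right, the SE ratio would be 1 and coverage would be 95%.

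**Effect on the conclusion.** At the stand-in ratios the raw difference is 1 − 0.40 = 0.60 or 1 − 0.44 = 0.56 of the CC mean. A correctly sized 95% half-width is at most about 0.11, so the direction would survive.

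**The case against.** A reader might infer that the SAP has chosen an untransformed analysis of CO and that its interval is therefore too narrow. The documents do not support that as a settled fact. The code cited in 12.6.2.1 takes logs, 12.6.2.1.1 says the secondary biomarkers are analysed on the log scale, the protocol agrees, and no departure is declared. The CO figure titled as an arithmetic mean belongs to the descriptive line graphs, not to the model. The omission may be a drafting slip.

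It can also be said that a log difference loses nothing, since 1 − exp(difference) is the percent reduction and the limits convert the same way. The table shells are in a separate document that may already provide for back-transformation. Exhaled CO lies outside the success criterion, which concerns the four primary markers.

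Most of this stands. It makes the fault a contradiction rather than a wrong choice, and it makes the interval problem conditional. It does not remove the fault, for two reasons. First, the sentence citing the 12.6.1.1 code cannot settle the scale, because the SAP uses it for analyses that are not on the log scale. In 12.6.3.4 it covers CYP2A6 change from baseline, which can be negative. In 12.6.3.6 it covers risk markers that are transformed only if they look non-normal. Second, the word difference is not evidently shorthand for a ratio: 12.6.3.2 logs the topography parameters, cites the same code and does promise a ratio.

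**Conclusion.** The concern holds as an internal contradiction. The CO paragraph of SAP 12.6.2.1 omits the log transformation that 12.6.2.1.1, protocol 12.4.4 and the cited code require, and the reporting sentence does not deliver the relative effects that the protocol promises. The last-measurement analysis also conflicts with section 9.

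The cost in precision is conditional. It arises only if the raw reading is followed with the common-variance code and CO variability rises in proportion to its mean with equal CV per arm. Under COHb ratios of 0.40 to 0.44, the standard error is then about 30% too small and coverage is about 82 to 85%. On the log scale coverage is 94 to 96% in the same scenarios.

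For the urinary markers, which are explicitly logged, interval width is not in question; only the tabulated measure is. The study's success criterion is untouched. The point is still worth settling, because CO carries a stated hypothesis and its scale should not be left to whoever writes the program.

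**What to change.** In SAP 12.6.2.1:

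- State that the log of the last Day 5 exhaled CO is modelled on the log of its time-matched Day 0 baseline, with sex, consumption and product as now.
- Add a rule for zero ppm readings, which have no logarithm. The zero-baseline rule in SAP section 7 covers percent change only, and the LLOQ/2 rule in 7.1 helps only if a quantification limit is defined for the breath device.
- Replace the reporting sentence with back-transformed geometric LS means and the THS 2.2 : CC and THS 2.2 : SA ratios with 95% CIs, for exhaled CO and every secondary urinary biomarker, as in 12.6.1.1.
- Say which CO analysis is the main one, the last measurement or the comparison over all time points, and align section 9 with it.

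The cost is SAP wording and matching table shells. The model code already exists, and no new data are needed. If the SAP can no longer be amended, its section 3 provides for describing the change in the study report.
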